3.6 Ethical and safety considerations

This work package involves adult participants, presumed to have mental capacity to make decisions relevant to participation in this study, who have assisted (CPR +/- AED use) at real-world cardiac arrests. This is a potentially sensitive topic, and the participant information includes numbers for support agencies. This includes GP, NHS 111 and telephone numbers and webpage contacts for MIND, Samaritans and Sudden Cardiac Arrest UK – the latter provides help and support to survivors and 'co-survivors' (people involved in a cardiac arrest) in the aftermath of the event. The senior research fellow conducting the interviews will also follow a 'Sensitive Call Action' procedure developed by Warwick Clinical Trials Unit (CTU) (**appendix 1**). This outlines clear actions that the interviewer can take should there be an immediate concern for the wellbeing of the interview participant, and may include the researcher asking a senior

member of staff from the University for help and/or calling 999. Should this occur, the researcher will notify the participant first. These options are made clear to the participant in the Participant Information Sheet. Our PPI representatives have reviewed this information.

In this work package, the risk to the interviewer is minimised by the remote nature of the interviews. However, this is still a sensitive topic. In the same way that the participant can, the senior research fellow can contact their GP, NHS 111 and access telephone numbers and webpage contacts listed in the Participant Information Sheet for MIND and Samaritans. They can also seek support from the University of Warwick's wellbeing services.

We will keep a record of any adverse events of which we become aware. If there are any Serious Adverse Events related to the interview, then we will inform the sponsor within 24 hours of us becoming aware, in line with University of Warwick SOPs.

We are interviewing people who responded in a 'Good Samaritan' role to an out-of-hospital cardiac arrest. We will not provide any medical advice, including advice about the management of cardiac arrest. We will also emphasise at the start of the interview that we are not in any way making judgements about what happened during their own experience, rather we are seeking to understand how we might optimise the use of drone-delivered AEDs in the future.

Remote interviewing, as well as being a pragmatic option, may result in a greater degree of actual or perceived anonymity (particularly with the option to turn cameras off). Additionally, when dealing with sensitive issues this may result in more honest or complete answers (41).

4. WORK PACKAGE 2

4.1 Objectives

Demonstrate capability for safe BVLOS flights of an AED-capable drone in controlled flight corridors.

Create compatible systems between drone operator and ambulance service; optimise automated drone-activation systems and flight start-up procedures once out-of-hospital cardiac arrest is identified during a 999 call.

Demonstrate an AED drone-delivery system that is fully integrated with ambulance service systems, in 'end-to-end' (from 999 call to AED use on a patient) BVLOS flights for simulated out-of-hospital cardiac arrests.

4.2 Development work

Demonstrate capability for safe BVLOS flights of an AED-capable drone in controlled flight corridors.

We have partnered with a UK drone company, SkyBound Rescuer (<https://SkyBoundrescuerproject.com/>), who specialise in using automated drones for public safety.

SkyBound have developed a comprehensive Operational Safety Case that details the testing of an AED-capable drone in BVLOS flight using dedicated air corridors. We will liaise with and receive all necessary approvals from the UK Civil Aviation Authority (CAA) to perform the drone flight required in this work package.

Create compatible systems between drone operator and ambulance service; optimise automated drone-activation systems and flight start-up procedures once out-of-hospital cardiac arrest is identified.

SkyBound and WAST have agreed a plan of work to integrate automated remote drone activation procedures with their Emergency Operations Centre, and to provide appropriate training in these procedures. Once an out-of-hospital cardiac arrest is identified during a 999 call and a request has been made to SkyBound's software, the drone can launch instantaneously and automatically. SkyBound and WAST will also develop communication procedures between drone operator and the Emergency Operations Centre during drone flight, thus providing the 999 call-handler with real-time information about the drone and its location that they can relay to the bystander at the scene of a cardiac arrest.

4.3 Approach and rationale

Demonstrate an AED drone-delivery system that is fully integrated with ambulance service systems, in 'end-to-end' BVLOS flights for simulated out-of-hospital cardiac arrests.

We have previously demonstrated that study participants can interact with a drone-delivered AED (19). What has not been tested before in the UK is a fully-integrated system that allows the BVLOS delivery of an AED via drone following diagnosis of cardiac arrest during a 999 call.

In this work package, we will ask study participants to come to the aid of simulated out-of-hospital cardiac arrest patients and to call '999'. The call will be directed to a WAST training call centre, which operates in the same way as a real 999 call, and used by us in our previous simulation study (19). In all other regards, the processes demonstrated in this work package (cardiac arrest diagnosis, automated drone activation, drone flight, real-time communications between drone and Emergency Operations Centre, AED delivery) will occur as they would in a real-world scenario.

When delivering an AED via drone, one important consideration is how long it takes a bystander to retrieve and attach the AED. Unnecessary delays in performing CPR can be detrimental to patient outcome, but potential delays caused by retrieving and using an AED must be balanced against the potential benefits of early defibrillation. Not all

patients in cardiac arrest will be suitable for defibrillation. It is not possible to know this in advance – an AED performs heart rhythm analysis and then shocks / does not shock according to its findings. Knowing how quickly a shock can be delivered and how long a bystander has to spend away from a patient to retrieve an AED will be an important consideration when implementing effective drone-delivered AED systems in the future.

Our previous simulation study demonstrated the importance of the bystander / 999 call-handler interaction in the process of retrieving and using a drone-delivered AED. This study will use information from audio/video analyses and from conversations to help ambulance services determine how best to communicate information about the arriving drone, and how best to offer advice during the 999 call about using an AED effectively.

Successful completion of this work package is one of the necessary pre-requisites for testing drone-delivery of AEDs for real-world out-of-hospital cardiac arrest. Other work is necessary too, such as modelling optimal locations for AED-capable drone sites so that a drone-delivered AED can reach a high proportion of patients in a suitable time-frame. Such modelling work is beyond the scope of this project but is planned for future work. It is feasible and has been conducted in other countries (9, 13, 42).

4.4 Study design

This will be an end-to-end test of drone-delivery of AEDs for simulated out-of-hospital cardiac arrest.

A study participant will find an adult ‘patient’ (a resuscitation manikin) in an outdoor location. They will be instructed only that: the person has collapsed in front of them and is not breathing and that they should call ‘999’. We will provide participants with a mobile phone with a pre-programmed number to make this call. The 999 call will connect to a WAST call-handler at a training centre.

The call-handler will handle it as a real-world call, asking questions, diagnosing cardiac arrest and providing telephone CPR instructions according to existing protocols. Once

cardiac arrest has been diagnosed during the 999 call, an automated instruction will be sent to a remote-located drone. This will start up, determine an appropriate flight-path and fly an AED to the cardiac arrest location. The drone pilot and 999 call-handler will have a 'live' line of communication during the flight.

The call-handler will inform participants that they have dispatched an AED via drone and update them when the drone's arrival is imminent. The drone will hover at the target location and lower the AED to the ground via winch. Video-recording equipment is integral to the drone and the drone operator can review in real-time that it is safe and appropriate to lower the AED to the ground. The winch will retract and the drone will hover above the AED to help indicate its location. The drone operator will indicate to the call-handler that it is safe to approach the drone, and the call-handler will relay this information to the participant. Once the participant has retrieved the AED the drone will start its flight back to its start location. The participant will then attach the AED to the patient. The AED will prompt them to deliver a single shock to the patient and the scenario will end.

The drone system will integrate with a commercial Unified Traffic Management (UTM) system (Guardian UTM) to simulate delays caused by receiving necessary BVLOS permission from the Civil Aviation Authority that would occur in unrestricted real-world flights outside of the designated corridor used for this study.

We can feasibly run six end-to-end scenarios per day. Each flight session (one day) will have received Civil Aviation Authority approval and will have a specific operational risk assessment prepared by SkyBound and the study team. We will rectify critical issues identified from participant feedback and by audio/video review after each flight session. Experience from our commercial partners suggests that for development of a system like this we will need up to four flying sessions, with critical issues identified in one session rectified before the next.

4.5 Participants and recruitment

We will recruit adults (≥ 18 years old) who:

The 3D Project Protocol

Version 3.0

IRAS Project ID: 318417

27 February 2024

Page 25 of 49

- have mental capacity to make decisions about study participation.
- believe themselves to have the physical and mental capability to perform CPR and use an AED in an outdoor environment.
- believe themselves able to use a mobile phone to communicate with a 999 call-handler.

We will **exclude** participants who are or who believe themselves to be pregnant, or those that are unable to complete the simulation because of physical or psychological distress.

Recruitment

We will recruit participants primarily by advertising via our contacts with WAST. We will seek the assistance of other groups such as Resuscitation Council UK and British Heart Foundation if necessary. We will also liaise with and advertise to local (to the simulation location) CPR training groups (e.g. St John, HeartStart) and other interested community groups. We will ask these organisations to send out a brief explanation of the project via email on our behalf, either as a standalone email or as part of a 'newsletter' or other regular update, according to their processes. We will also advertise the project using the institutional social media accounts of the research collaborators and the organisations mentioned above, according to each's social media policies. The organisations mentioned have diverse memberships and we will liaise closely with our PPI co-applicants to ensure that recruitment materials are accessible and relevant to all members of the communities that we serve.

We will look to recruit some participants who have had CPR/AED training (+/- have real-world experience of performing CPR and/or using an AED) and some who have not. A 2017 survey of UK adults showed that 40% of the adult population had not been trained in CPR, and 80% had not been trained in AED use (43). If, during the recruitment process, we note that we are disproportionately recruiting either trained or untrained participants, we will adjust our advertisement process so that we subsequently recruit only from the under-represented group.

All recruitment advertisements will include contact details for the study team. For those who contact us and express a willingness to proceed, we will send out a study participant information sheet and consent form using SharePoint via Teams. A secure SharePoint/Teams link with access restrictions and permissions will be sent from a University of Warwick institutional email in order that potential participants can familiarise themselves with the study details and the statements on the consent form. Correspondence via SharePoint/Teams will include information on the date/time and exact location of the study. We will confirm that they meet the eligibility criteria at this point.

We will send one e-mail reminder to those who express an initial interest in the study but then do not follow-up one - two weeks after we have sent out the Participant Information Sheet and consent form.

We will ensure that participants have adequate time to consider participation, ask questions and have them answered to their satisfaction, and to complete the consent form. On the study day itself we will re-confirm eligibility, answer any further questions and obtain written consent. We will then proceed with the simulation.

We anticipate that simulations will take up to 30 minutes to complete. We will ask people to arrive 30 minutes before the start of the simulation, and the post-simulation questionnaire and conversation will take no more than 15 minutes. Even allowing for delays, participants will spend a maximum of 90 minutes at the simulation site – it may well be far less. We refer to our previous drone simulation study experience when making these estimates (19). Participants will be able to stop the simulation at any point if they feel unable to continue. We will have a live communication channel to the drone pilot to inform them if this happens before the drone arrives so that the drone pilot can recall the drone to its base.

Participants will be able to withdraw from the study at any time. If they withdraw after we have analysed their post-event conversations and audio/video files associated with a particular simulation, we may not be able to identify exactly how all information that came from one participant contributed to and influenced our overall conclusions. We

will not keep information about them that we already have unless they withdraw after we have completed quantitative analyses and submitted them for publication or other output. We will securely delete audio and video recordings once we have completed and documented our analysis of them. Participants will be offered a voucher to the value of £25, even if they do not complete the simulation or subsequently withdraw their consent after the simulation has finished.

Sample size

In our previous simulation study we recruited 18 participants without difficulty and gathered a wealth of information about how processes surrounding AED delivery by drone might be optimised (19). Given this and the daily maximum limit on flights, we have set an *a priori* sample size of 20 participants here.

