1.3 The need for this study

Barriers to public-access AED use

The NHS Long Term Plan aims to improve the public-access AED network to help save 4,000 additional lives each year from cardiac arrest, and to reduce health inequalities (21). However, public-access AEDs in the UK are not optimally nor equitably placed. AED density (per square-km) varies by geographical region (lowest in North-East England), by affluence (fewer in poorer areas) and by population density (fewer where residential density is higher) (22). Areas of low AED density correlate closely with areas of high out-of-hospital cardiac arrest incidence and low bystander CPR rates, further exacerbating this inequity (6).

Our systematic review synthesised data from 68 studies to characterise facilitators and barriers to successful bystander AED use (23). Several key barriers relate to the static location of AEDs and the need for bystanders to leave a patient to retrieve one.

The path to successful public-access AED is a complicated one. First, one must determine whether an AED is close enough to retrieve and use. Where only a single bystander is present, there is a need to balance benefits of early defibrillation against harms of not delivering prompt CPR. A bystander must be able to successfully locate,

retrieve and then use a public-access AED. Studies highlight that bystanders are often reluctant to leave a patient (24, 25), and the further away a patient is from a public-access AED the less likely it is that one will be used (26).

The importance of overcoming these barriers

Direct delivery of AEDs via drone to members of the public attending an out-of-hospital cardiac arrest may be a way of overcoming the barriers to public-access AED use. Other countries have demonstrated the concept and there is real-world use in Sweden. Developing a system in the UK, and using the experience of others to optimise communications between ambulance services and drone operators, is an area ripe for immediate further study.

Survival with favourable neurological outcome is an important outcome for both patients and their relatives (27). A recent collaboration between adult out-of-hospital cardiac arrest survivors, their families and the James Lind Alliance reported that optimising community interventions and focussing on longer-term impacts were top priorities (28).

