Appendix 3 – Post-event conversation questions (work package 2)

PARTICIPANT NUMBER _____

Age (in years) _____

Gender (M, F, identifies another way – specify) _____

Training in last five years (Yes/No)

CPR only _____

AED only _____

Both _____

Real-world experience in last five years (Yes/No, number of occasions if yes)

CPR only _____

AED only _____

Both _____

Opening question:

- “What are your thoughts on how that went?”

Probing questions (if needed):

- “Did you encounter any difficulties in retrieving the defibrillator?”
- “Is there something that would make it easier for you to retrieve the defibrillator”

Closing question:

- “Is there something else you would like to add to your answers so far?”

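### Work package 2 neither excludes nor identifies repeat participants from the team's earlier drone-AED simulation, and does not record a professional resuscitation role, so participant-dependent timings could look somewhat favourable (minor; cheap to fix).

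*Protocol*

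**What the plan says.** - **Intended user.** Protocol section 1.3 motivates the work by "Direct delivery of AEDs via drone to members of the public attending an out-of-hospital cardiac arrest". Section 4.3 treats speed of shock delivery and time spent away from the patient as bystander quantities that will inform later implementation.
- **Recruitment (section 4.5).** The main route is "We will recruit participants primarily by advertising via our contacts with WAST". Local "CPR training groups (e.g. St John, HeartStart) and other interested community groups" are also approached. Social media is a further route: "We will also advertise the project using the institutional social media accounts of the research collaborators and the organisations mentioned above".
- **Eligibility (section 4.5).** Inclusion needs adulthood, capacity, self-rated ability to do CPR and use an AED outdoors, and self-rated ability to speak to a call-handler by phone. The exclusions are "participants who are or who believe themselves to be pregnant, or those that are unable to complete the simulation because of physical or psychological distress".
- **Training mix (section 4.5).** "We will look to recruit some participants who have had CPR/AED training", and some who have not. If either group is over-represented, recruitment moves to the other. No target share or threshold is given.
- **What is recorded (section 4.6, Appendix 3).** Age, gender, CPR/AED training in the last five years as yes/no, and "Real-world experience in last five years (Yes/No, number of occasions if yes". There is no item on occupation or on earlier participation.
- **Earlier study (sections 1.2, 4.3, 4.5).** Participants made a simulated 999 call, gave CPR and were told that an AED would come by drone. The same training call centre was used. On numbers: "In our previous simulation study we recruited 18 participants without difficulty".

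**The concern.** Two kinds of participant could perform better than the first-time lay user for reasons unrelated to the delivery system.

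The first is anyone who has already done the task. The main behavioural finding of the earlier simulation was hesitation: people were uneasy about leaving the patient and sought the call-handler's permission (sections 1.2 and 3.2). In the new scenario participants are told little beyond the collapse and the need to call 999 (section 4.4). A returning participant knows what comes next, so part of that hesitation may be gone.

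The second is a person with a professional resuscitation role whose recent record does not reveal it, such as an instructor, or a staff member with few recent events.

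The outcomes at stake are those that depend on the participant: hands-off CPR time, time away from the patient, arrival to attachment, call to application and shock, and the usability score. Section 4.7 reports timings and score as median and interquartile range. If the information is not collected, no later analysis can separate these people.

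**Working it through.** **1. Who can enter and who can be identified**

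| Type of participant | Excluded by section 4.5? | Visible in section 4.6 or Appendix 3? |
|---|---|---|
| Took part in the earlier simulation | No | No |
| Professional, many recent resuscitations | No | Largely, through the number of occasions |
| Instructor or staff member, few recent events | No | No; looks like any trained lay person |
| Lay person, trained or untrained | No | Yes, through the training item |

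The training-mix rule limits professionals, because they can fall only in the trained group. It does not identify them: training is yes/no, so a paramedic and someone who attended one course count alike. It does not address earlier participation.

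**2. The plan's own figure.** The sample size is 20, justified by experience and capacity, with no precision target, so there is no statistical figure to reproduce. Capacity is 6 scenarios per day × up to 4 sessions = 24 slots, so 20 fits.

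**3. Illustrative size, hands-off time**

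Input from section 1.2: median 109 s, interquartile range 87–130 s, 18 simulations. Under normality, SD = (130 − 87)/1.349 = 31.9 s.

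Assumptions not in the protocol: the 109 s describes first-time lay users, a share p of the sample is faster by d seconds, and the spread is the same. The pooled median m solves

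(1 − p)·Φ((m − 109)/31.9) + p·Φ((m − 109 + d)/31.9) = 0.5

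| Share p (of 20) | d = 10 s | d = 30 s | Fall from 109 s |
|---|---|---|---|
| 10% (2) | 108.0 | 106.3 | 1.0–2.7 s |
| 25% (5) | 106.5 | 101.9 | 2.5–7.1 s |
| 50% (10) | 104.0 | 94.0 | 5–15 s |

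A stronger assumption, with the faster group centred at 60–80 s and SD 15.9 s, gives about 105 s at 10%, 96–99 s at 25% and 84–93 s at 40%.

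**4. Compared with sampling error.** The large-sample standard error of a median is 1.253 × 31.9/√20 = 8.9 s. Simulating medians of 20 from the same normal distribution gives 8.6 s, with a 95% range of about 92–126 s. Every 10% and 25% result above lies inside that range, under both assumptions. Only a large share combined with a large advantage would move the median outside it.

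**5. Outcomes little affected.** Call to ready-for-flight, start of flight and total flight time depend mainly on the call-handler, the airspace approval step and the drone.

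**The case against.** The case for leaving the plan alone is substantial.

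- **Experience is recorded.** Appendix 3 counts real CPR/AED occasions over five years, and 20 records can be read one by one. Someone who resuscitates for a living would stand out. This stands, and it narrows the gap to repeat participants and low-exposure professionals.
- **Routes are wider than the ambulance service.** Community groups and social media are used. For work package 1, section 3.4 describes the ambulance service's contacts as survivor and bystander groups, which are lay networks. A reader might infer from section 4.5 that the sample will be largely ambulance staff. The protocol does not support that: nothing says the adverts target staff.
- **The training-mix rule limits contamination.** If trained and untrained groups were equal (an assumption), a 40% share of professionals would need 8 of the 10 trained places. This also stands, although the rule has no number attached.
- **Repeat participation is conjecture.** At most 18 people are concerned, and the protocol does not say that they will be approached. True, but nothing prevents it or would reveal it.
- **The design is descriptive.** There is no comparison or test, and the aim is to improve the process between sessions. This keeps the point minor. It does not change that the timings are read as bystander timings.
- **Off-duty professionals can be bystanders.** This is a fair reason not to exclude them outright.

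**Conclusion.** The point holds as a minor, cheap improvement. Earlier participation is neither excluded nor recorded, and professional role is not recorded. The existing items on training and experience and the balancing rule cover the second gap only in part and the first not at all.

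The likely direction is towards shorter participant-dependent timings and a better usability score. That rests on reasoning about familiarity and skill, not on data in the protocol. The size cannot be derived: neither the share of such participants nor their speed advantage is given, and section 1.2 does not say who the earlier study's participants were, so even the 109 s starting value is assumed to be lay. At low shares the shift would lie within sampling error for 20 people.

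A reader might go further and conclude that the reported timings will be materially too short, or that professionals could not be told apart at all. The first is not shown. The second is contradicted by the recorded number of real events.

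**What to change.** 1. Add to the section 4.5 exclusions: took part in the earlier drone-AED simulation. The eligibility checks already planned before and on the study day can carry the question.
2. Add one item, at screening or in Appendix 3, on current or former occupation with resuscitation duties.
3. Report the participant-dependent timings and the usability score with and without participants who have such duties. Launch and flight times need no split.

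Excluding professionals altogether is not needed for this.

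Cost: at most 18 people leave the pool, one extra question is asked, and a few extra summary lines are reported. With 20 participants the second set of summaries will be imprecise and should be presented as descriptive.
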